## Methods

---

### Participants

Older adults (> 55 years) will be recruited from the University of Illinois Hospital Geriatric Clinic and flyers in nearby independent living senior centers and grocery stores. We expect ten older adults participated in the study after obtaining a written informed consent.

### Participants' eligibility

To be included, participants must score 18-24 out of 30 on the Montreal Assessment on Cognitive Assessment (MoCA). Participants with uncontrolled cardiovascular disease, presence of any neurological condition (e.g., Alzheimer's disease), and/or severe musculoskeletal diseases that may interfere with the ability to receive the intervention were excluded. Additionally, people with the inability to stand independently without an assistive device for the length of a Wii-Fit game, with a fracture risk heel bone density (measured using Lunar Achilles Insight) T-score < -2.0, and inability to communicate and understand English were excluded.

### Research Design

This study will be a single arm pre-post research design consisting of 4 weeks of DT exergaming sessions. Baseline (at week 0) and post-testing (at 5th week) outcome measures will be collected.

### Intervention

In total, 12 sessions of individual one-on-one DT exergaming will be administered and supervised by a research personnel (physical therapist) in a research facility. Participants will wear a gait belt and were supervised during the session. DT exergaming will be delivered via Wii-Fit standing balance games which was performed at light intensity (rate of perceived exertion via Borg's scale with individuals reporting score of 7-11) (17) and will be concurrently performed with explicit cognitive games (therapist cued) for 90 minutes/session, 3 times/ week. While Wii fit games will implicitly address cognitive domains like working memory, episodic memory, and visuospatial awareness, explicit cognitive games targeted subdomains of executive function – working memory and attention, and semantic memory, abstract memory. Warm up (step-in-place, trunk twists) and cool down (stretching of lower limb) will be performed before and after session, respectively. Refer to supplementary material section for details of protocol.

## Assessments

Volitional balance control task: The limits of stability (LOS) test via Balance Master (Equitest® Neurocom) (18) will be administered. Participants will be secured in a safety harness and asked to stand on the force platform of the Balance Master (Figure 1). Participants will be instructed to lean their body either in the forward, backward, left, or right direction to move their center of gravity (COG) projection shown on a screen to the desired direction without losing balance, stepping, or reaching for assistance.

[figure not shown]

Figure 1

Represents a picture of an individual performing the limits of stability test on Balance Master (Equitest® Neurocom) in the forward direction

## Cognitive task

Auditory clock test (ACT) (19) and letter number sequencing task (LNS) (20) will be administered using the DirectRT EmpirisoftTM (21) software to assess subdomains of executive function (visuo-spatial memory, working memory, attention, and cognitive flexibility). The audio

cues will be delivered through headphones and responses will be recorded through a microphone. The ACT involves responding to different times of the day, “yes” if the hour and the minute hand was on the same side of the clock face and “no” otherwise. The LNS will involve sequentially listing alternate letter and number combinations, for example, response to “C5,” was D6, E7, etc.

## Interference test

The LOS test (all directions) will be performed along with both cognitive tasks mentioned above. Participants will began responding to the cognitive cues followed by the LOS task.

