## Outcome measures

Volitional balance control and interference task: Single task (task when performed alone) and performance during interference task was quantified by the movement stability measurement of maximum excursion (MXE, expressed in percentage), which is the maximum ability to shift one’s COG toward the theoretical limit in the desired direction. Higher values indicate better performance.

Cognitive and interference task: Accuracy  $[(\text{Correct responses}) / (\text{Total responses}) * 100]$  was calculated during single and interference task.

NIH toolbox: Speed (m/sec) for 4-meter gait test and distance covered in 2-minute walk test for endurance will be computed. Number of correct responses for list sort memory test and accuracy for the remainder tests was included for analysis.

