## Statistical analyses

Statistical analyses will be performed using SPSS version 24, Chicago, IL, USA. For MXE in each volitional balance control task direction (i.e., forward, backward, left, and right), 2 x 2 repeated measures analysis of variance (ANOVA) will be performed to examine the time (pre- to post-training) and task (single vs. interference task) differences on with follow-up post-hoc tests. Similarly, four repeated measures ANOVA for accuracy (cognitive) in ACT and LNS will be performed. Paired t-test will be conducted for NIH toolbox measures. Refer supplementary material section for detail

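### Does the unstated order of single-task and interference tests undermine the task comparison in the ANOVAs?

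*Combined protocol and SAP*

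**What the plan says.** Each participant leans in four directions on the Balance Master; the Assessments section tells them to "lean their body either in the forward, backward, left, or right direction". ACT and LNS are given as cognitive tasks. The Interference test section then combines the two: "The LOS test (all directions) will be performed along with both cognitive tasks mentioned above". Its only remark on sequence is "Participants will began responding to the cognitive cues followed by the LOS task", which reads as the start order inside one combined trial, not the order of conditions across the session.

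Under Outcome measures, balance is taken in both conditions ("Single task (task when performed alone) and performance during interference task was quantified by the movement stability measurement of maximum excursion"), and cognitive accuracy likewise "was calculated during single and interference task". The Statistical analyses section fits a 2 x 2 repeated measures ANOVA for each direction to "examine the time (pre- to post-training) and task (single vs. interference task) differences", and similar ANOVAs for ACT and LNS accuracy. There is no order term. The Intervention, NIH Toolbox and Statistical analyses sections refer the reader to supplementary material that is not part of the supplied text.

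The Research Design section is explicit that there is no control group: "This study will be a single arm pre-post research design consisting of 4 weeks of DT exergaming sessions". Testing takes place at week 0 and in week 5, and ten participants are expected.

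**The concern.** A within-person comparison of two conditions is only as clean as the order in which they are run. Repetition is built into each visit. If every combination is run once, there are 4 + 4 + 4 = 12 leans (alone, with ACT, with LNS) and 1 + 4 = 5 runs each of ACT and LNS (alone, then with the four directions). The one-run reading is an assumption; the text gives no trial counts.

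If all participants did the single tasks first, the interference condition would always come later in the session. Practice would then flatter interference performance and hide a dual-task cost; fatigue would create or enlarge one. The two explanations cannot be separated afterwards, because condition and position are the same variable when only one order is used. A significant task effect might not be a dual-task cost, and a real cost might be missed. Since order has to be settled before the first participant is tested, it is natural to ask for a balanced order and a matching model term.

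**Working it through.** The plan gives no power, significance level, SD or effect size, so it has no figure to reproduce. What follows shows which effects a fixed order touches, and how strongly under assumed shifts.

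**Inputs.** From the documents: n = 10; two visits; two task conditions per person per visit. Assumed: two-sided 5% level; a position shift g (later minus earlier condition), in units of the SD of each person's task difference averaged over visits; values of g from 0.3 to 0.5.

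**Which effects are touched.** Let D_v be interference minus single at visit v, with true task effect τ_v. With single tasks first for everyone and shift g_v, the mean of D_v is τ_v + g_v.

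- Task main effect: (D_0 + D_5)/2 has mean (τ_0 + τ_5)/2 + (g_0 + g_5)/2. If g_0 = g_5 = g, the bias is g.
- Time by task: D_5 - D_0 has mean (τ_5 - τ_0) + (g_5 - g_0). With equal shifts the bias is 0.
- Time main effect: the shift enters only the interference half of each visit mean, so the bias is (g_5 - g_0)/2, again 0 with equal shifts.

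Simulating the full 2 x 2 layout with equal shifts of 0.3 and 0.5 agrees. Rejection rates are 13.6% and 29.3% for task, 5.1% and 4.9% for time, and 5.0% and 5.1% for the interaction.

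**Size for the task effect under a fixed order.** The task test is a one-sample t-test on the person-level difference, with noncentrality d√10 on 9 degrees of freedom.

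| Situation | Net d | Probability of significance |
|---|---|---|
| No true cost, shift 0.3 | 0.3 | 13.6% |
| No true cost, shift 0.5 | 0.5 | 29.3% |
| True cost 0.8, no shift | 0.8 | 61.6% |
| True cost 0.8, opposing shift 0.3 | 0.8 - 0.3 = 0.5 | 29.3% |
| True cost 0.8, opposing shift 0.5 | 0.8 - 0.5 = 0.3 | 13.6% |

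**What counterbalancing would buy.** Take a 5/5 split (single-first or interference-first) with order in the model, leaving 8 degrees of freedom.

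- Symmetric shift: the bias is 0, type I error is 5.0%, and power at 0.8 SD is 60.3%. The extra term costs little.
- Shift in one order only: the two order groups have biases s and 0, so their unweighted mean keeps s/2. At s = 0.5 the remaining bias is 0.25 SD, and rejection with no true cost is 10.8%, against 29.3% under a fixed order.
- Uneven dropout: with 5 and 3 completers, the unweighted mean has variance (1/5 + 1/3)/4 = 1/7.5. Power at 0.8 SD on 6 degrees of freedom is 45.3%. Eight completers under one fixed order would have 49.6% on 7 degrees of freedom, so most of the fall from 60.3% comes from losing two people, not from the order term.

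**What the figures do not show.** They describe a t-test with ten people under shifts chosen for illustration. Nothing in the documents says that the order is fixed or that a shift exists.

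**The case for a change.** The case for a change is respectable. The plan tests task as a factor, the visible text leaves the order open, and the aliasing under a common order is exact. The remedy needs only an allocation list and one model term, with no extra visits or participants. Full counterbalancing of every condition is not required: spreading ten people 3/2/2/3 over the four sequences (single-first or interference-first, crossed with ACT-first or LNS-first) gives 5/5 on each factor. All of that stands as conditional reasoning, and the arithmetic is right.

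It does not establish a defect. The plan states no wrong rule; it leaves a procedural detail out of the main text while sending detail to a supplement. The Interference test section does not itself cite that supplement, so this is a possibility, not proof that the order is given there.

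Nor is the remedy plainly better. Doing each task alone before combining them is a defensible sequence for people with MoCA scores of 18-24. Interference-first would have half of them meet the combined task cold, and that is a plausible source of the asymmetric carry-over of which the balanced design removes only half.

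A separate worry is that retest gain enters the pre-post contrast and the Toolbox comparisons ("Paired t-test will be conducted for NIH toolbox measures"). It has nothing to do with test order. The single arm is openly declared, and the visible text does not attribute the change causally to training, so there is no wording to correct.

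**Conclusion.** No change to the plan follows. The visible text omits the order of test conditions, and under one common order the task main effect, with its single-versus-interference follow-up tests, includes any position effect in full. At assumed shifts of 0.3 to 0.5 SD, that means 14% to 29% significant results with no true cost, or power of 29% down to 14% instead of 62% for a true cost of 0.8 SD. These figures rest on an undocumented fixed order, an undocumented shift and an assumed 5% level.

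The point is minor because the training contrasts are spared when the shift is additive and equal at both visits. That protection would weaken if a person's order differed between visits or if practice or fatigue changed by week 5; the interaction would then be biased by the change in shift, and the time effect by half of it.

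Analysts can be expected to fill the gap sensibly: record the order used, keep it the same for each participant at both visits, and read the task main effect as including any order effect if the order was common to all. Counterbalancing with an order term would be worth weighing if dual-task cost were itself the intended conclusion, but it is a trade-off and not a correction.

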## NIH Toolbox

An iPad will be used to test the motor and cognitive domains. The motor tests will include 4-meter gait speed test and 2-minute walk test. The cognitive tests include list sort memory test (working memory), picture sequence memory test (episodic memory), dimensional change card sort test (executive function), flanker inhibitory control and attention test (attention and executive function), and pattern comparison processing speed test (processing speed) (refer supplementary material section).

## Outcome measures

Volitional balance control and interference task: Single task (task when performed alone) and performance during interference task was quantified by the movement stability measurement of maximum excursion (MXE, expressed in percentage), which is the maximum ability to shift one’s COG toward the theoretical limit in the desired direction. Higher values indicate better performance.

Cognitive and interference task: Accuracy  $[(\text{Correct responses}) / (\text{Total responses}) * 100]$  was calculated during single and interference task.

NIH toolbox: Speed (m/sec) for 4-meter gait test and distance covered in 2-minute walk test for endurance will be computed. Number of correct responses for list sort memory test and accuracy for the remainder tests was included for analysis.

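### Pattern comparison, the only Toolbox test labelled processing speed, is scored by an accuracy that the supplied text does not define; read as correct/total responses, it cannot register a pure speed gain

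*Combined protocol and SAP*

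**What the plan says.** The NIH Toolbox section lists two motor tests and five cognitive tests, each cognitive test with its domain in brackets. Only one has speed as its domain: "pattern comparison processing speed test (processing speed". That entry is followed by a pointer to supplementary material.

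The Outcome measures section then sets the scores: "Number of correct responses for list sort memory test and accuracy for the remainder tests was included for analysis". List sort is scored by a count. The other four cognitive tests (picture sequence, card sort, flanker and pattern comparison) are scored by accuracy. For pattern comparison no response time, count per unit time or derived score is named.

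The one accuracy formula in the document stands one paragraph earlier, under the cognitive and interference tasks: correct responses divided by total responses, times 100. Its stated scope is that it "was calculated during single and interference task", which means the auditory clock test (ACT) and letter number sequencing (LNS).

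The Statistical analyses section says: "Paired t-test will be conducted for NIH toolbox measures". It ends with "Refer supplementary material section for detail".

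**The concern.** A processing-speed test is informative because it shows how much correct work is done per unit of time. A ratio of correct to attempted responses removes the amount of work and keeps only the error rate. An analyst who meets the word accuracy in the Toolbox paragraph, just after the only definition of it, could reasonably apply that definition. The contrast drawn with number of correct responses for list sort also suggests that something other than a count is meant.

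If so, the t-test on pattern comparison could mislead in both directions. A real gain in speed could leave the score unchanged, and a slowdown with fewer errors could raise it. The battery would then hold a test labelled processing speed whose result says nothing reliable about speed.

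**Working it through.** The plan gives no figure on this point, so there is none to reproduce. The check is algebraic, followed by two worked cases.

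**Inputs from the document**
- Score for pattern comparison: accuracy, with no Toolbox definition (Outcome measures).
- Only available formula: A = 100 × C/T, where C is correct responses and T is total responses (Outcome measures, written for ACT and LNS).
- Analysis: paired t-test before versus after training (Statistical analyses).

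**Assumed inputs**
- That the formula applies to pattern comparison.
- That the number of items answered can vary, as in a timed test. The document does not describe the test format.
- All response counts below, and a fixed item total of 60 used for contrast.

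**General result.** Let a participant answer g times as many items at the same proportion correct p. Then T becomes gT, C = pT becomes pgT, and A = 100 × pgT/(gT) = 100p. The factor g cancels, so the change in score is zero for any speed gain. This does not depend on the counts chosen.

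**Case 1: faster, same error rate**
- Before: 30 correct of 32, A = 100 × 30/32 = 93.75%.
- After: 45 correct of 48, A = 100 × 45/48 = 93.75%.
- Change in A: 0. Change in number correct: 45/30 = 1.5, that is 50% more.

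**Case 2: slower, more careful**
- Before: 36 correct of 40, A = 90.0%.
- After: 29 correct of 30, A = 96.7%.
- Change in A: +6.7 points. Items answered: 30/40 = 0.75, that is 25% fewer. Number correct falls from 36 to 29.

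**Contrast: fixed denominator.** If accuracy means correct out of a fixed total within a time limit, the score does carry speed. With a total of 60:
- Case 1 goes from 30/60 = 50.0% to 45/60 = 75.0%.
- Case 2 goes from 36/60 = 60.0% to 29/60 = 48.3%.

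Such a score is number correct divided by a constant, so its paired t statistic equals that of number correct. The whole question therefore turns on the denominator, which the supplied text does not give.

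**The case against.** The strongest reply is that the document never applies the ACT/LNS formula to the Toolbox. The formula belongs to a separate paragraph with its own scope, and the Toolbox tests come with a reference to supplementary material, the natural place for scoring rules. That stands, and it is why the point is conditional. It also means that accuracy is undefined only in the supplied text, not necessarily in the full plan.

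A second reply is that the format of the test is assumed: nothing says it is timed, that item counts vary, or what the iPad records. This also stands, and the fix has to allow for it.

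A third is that the supplied text states no processing-speed hypothesis and ties no decision to this t-test, so reporting accuracy as accuracy would be legitimate. That is right, provided it is labelled so.

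A fourth is that the definition gap is shared by all four tests scored by accuracy. It is, but pattern comparison is the one whose stated domain is speed, so it is where the choice of denominator most directly changes what is measured.

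A reader might go further and infer that the plan has adopted a score blind to speed, or that the trial will miss a speed benefit with some calculable probability. The documents support neither. The first needs the formula to be carried across paragraphs. The second needs item counts, error rates and variances that the documents do not give; only the expected sample of ten is stated.

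**Conclusion.** The point holds in conditional form, with medium confidence. The supplied text scores its only test labelled processing speed by an accuracy it does not define. If that accuracy is correct over total responses, the score is exactly unchanged by a pure speed gain and can rise when responding slows, so the paired t-test cannot be read as a test of processing speed. A change in the proportion correct would still register, up to the 100% ceiling. If accuracy is correct out of a fixed total within a time limit, the score does carry speed, and the remaining defect is only that the plan does not say so.

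The cancellation is exact; the counts that illustrate it are assumptions. The scope is small: one of seven Toolbox measures (two motor plus five cognitive), none given priority, in a study of which the Participants section says "We expect ten older adults participated in the study" and the Research Design section says "This study will be a single arm pre-post research design". Maximum excursion and the ACT and LNS scores are unaffected. It should be fixed because it is cheap to fix, not because it threatens the study as a whole.

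**What to change.** In the Outcome measures section, settle the pattern comparison score before the data are examined, by whichever of these applies:

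1. Name a score that carries speed: number correct in the test time if the test is timed, or response time on correct items, whichever the device records.
2. If accuracy already means correct out of a fixed item total within a time limit, state that definition and its denominator.
3. If only correct over attempted is available, call the outcome pattern comparison accuracy and draw no processing-speed conclusion from it.

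The same sentence could usefully give the denominator for the other three tests scored by accuracy.

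The cost is a wording change and possibly a different exported score, assuming the device stores counts or response times, which the document does not say. No new procedure, visit or participant is needed, and the paired t-test can stay.

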## Statistical analyses

Statistical analyses will be performed using SPSS version 24, Chicago, IL, USA. For MXE in each volitional balance control task direction (i.e., forward, backward, left, and right), 2 x 2 repeated measures analysis of variance (ANOVA) will be performed to examine the time (pre- to post-training) and task (single vs. interference task) differences on with follow-up post-hoc tests. Similarly, four repeated measures ANOVA for accuracy (cognitive) in ACT and LNS will be performed. Paired t-test will be conducted for NIH toolbox measures. Refer supplementary material section for detail

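### At least 15 pre-post tests on ten people in a single arm, with no primary test, multiplicity correction or exploratory label in the text available

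*Combined protocol and SAP*

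**What the plan says.** The Research Design section describes a single-arm, pre-post study, and the Participants section expects ten people. The Statistical analyses section sets out three groups of tests.

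- **Maximum excursion (MXE).** There is one two-by-two repeated measures ANOVA per direction: "For MXE in each volitional balance control task direction (i.e., forward, backward, left, and right". Its stated purpose is "to examine the time (pre- to post-training) and task (single vs. interference task) differences on with follow-up post-hoc tests".
- **Cognitive accuracy.** "Similarly, four repeated measures ANOVA for accuracy (cognitive) in ACT and LNS will be performed".
- **NIH Toolbox.** "Paired t-test will be conducted for NIH toolbox measures". The NIH Toolbox section lists two motor tests ("The motor tests will include 4-meter gait speed test and 2-minute walk test") and five cognitive tests. The Outcome measures section gives each motor test one result and, for the cognitive tests, says: "Number of correct responses for list sort memory test and accuracy for the remainder tests was included for analysis".

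The Interference test section adds that "The LOS test (all directions) will be performed along with both cognitive tasks mentioned above", so there are two interference conditions. The analysis section does not say how these two enter the two-level task factor.

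The analysis section ends with "Refer supplementary material section for detail". That supplement was not available for this review, nor were the opening pages of the document. The remaining text contains no primary outcome, primary contrast, significance level, multiplicity correction or exploratory label.

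**The concern.** With no control arm, any claim of benefit rests on the pre-post tests. If none is singled out in advance, a reader of the results cannot tell a planned finding from the best of 15 or more.

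A second problem lies in the choice of contrast. The plan names time differences and task differences but not their interaction, and it does not say which post-hoc comparisons are run or what triggers them. The time main effect averages single-task and interference performance. A significant time effect is therefore not, by itself, evidence of better balance or accuracy under interference, which is the condition closest to what dual-task training aims at.

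**Working it through.** The plan gives no significance level, power or number of tests, so there is no stated figure to reproduce.

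**Inputs from the documents:** n = 10; four MXE directions; four accuracy ANOVAs; 2 + 5 = 7 Toolbox measures; two named effects per ANOVA (time, task).

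**Assumed, because not stated:** two-sided 0.05 per test; all effects null; a common correlation between outcomes of 0, 0.3, 0.5 or 0.7.

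**Step 1: count.** Number of tests = ANOVAs x effects per ANOVA + Toolbox t-tests.

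| Reading | ANOVAs | Time tests | Time and task | With interaction |
|---|---|---|---|---|
| Literal | 4 + 4 = 8 | 8 + 7 = 15 | 8 x 2 + 7 = 23 | 8 x 3 + 7 = 31 |
| MXE analysed separately for the two interference conditions | 8 + 4 = 12 | 12 + 7 = 19 | 12 x 2 + 7 = 31 | 12 x 3 + 7 = 43 |
| As above, and four accuracy ANOVAs per cognitive task | 8 + 8 = 16 | 16 + 7 = 23 | 16 x 2 + 7 = 39 | 16 x 3 + 7 = 55 |

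Post-hoc tests come on top. The time tests are the column that matters for a claim of benefit.

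**Step 2: chance of at least one false improvement among the time tests.** With two levels per factor, each time effect is a t-test on 9 df of a per-person change. At two-sided 0.05, the chance of a false improvement in one such test is 0.025. With k independent tests the chance of at least one is 1 - 0.975^k:

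- k = 15: 1 - 0.975^15 = 0.316
- k = 19: 1 - 0.975^19 = 0.382
- k = 23: 1 - 0.975^23 = 0.441

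For correlated outcomes the figures come from 200,000 simulated null trials of ten people with equal correlation between outcomes.

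| Time tests | Corr. 0 | 0.3 | 0.5 | 0.7 |
|---|---|---|---|---|
| 15 (literal) | 32% | 25% | 20% | 14% |
| 19 | 38% | 29% | 22% | 16% |
| 23 | 44% | 32% | 25% | 17% |

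One pre-named test gives 2.5%.

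**Step 3: what the time effect measures.** Let S be a person's pre-post change in single-task performance and I the change under interference. The time effect tests the mean of (S + I)/2, and the interaction tests the mean of I - S. If S has mean 1 and I has mean 0, the time effect has mean (1 + 0)/2 = 0.5. It is then truly non-zero although nothing changed under interference. Only a test of I answers the interference question directly, and only the interaction tests whether the two changes differ.

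**The case against.** **The supplement may settle it.** The analysis section defers to supplementary material, and the opening pages were not available. A reader might infer that the trial has no primary outcome at all. The documents do not support that; they support only that none is found in the text available. This limits confidence to medium.

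**A ten-person study may properly be exploratory.** That is fair, and the available text states no confirmatory hypothesis. But the analysis section does not say the tests are exploratory, and saying so is itself one of the remedies.

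**The number of tests can be made to look worse than it is.** A reader might take the full 23 and quote the chance of any false positive under independence, 1 - 0.95^23 = 69%. Eight of those 23 are task effects (single task against interference) that carry no claim of benefit. The figure also counts false worsening and ignores correlation within the same ten people. The 15 time tests are the fair basis.

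**Post-hoc tests may guard against misreading the time effect.** A reader might infer that a time effect would often be mistaken for a gain under interference. Suppose only single-task performance improves, by an assumed 1 SD of change. A significant time effect with a non-significant interaction then occurs in about 25%, 14%, 7% or 2% of trials at correlation 0, 0.3, 0.5 or 0.7 between the two changes. That holds only if no post-hoc test of the interference change is run, and the plan does provide for unspecified post-hoc tests. If that test must also be significant, the figures fall to about 2%, 2%, 1% and under 0.5%. What stands is that the interaction and the post-hoc comparisons are not named, not that the plan misleads at a known rate.

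**The 2.5% comparator is for the primary test alone.** Any secondary tests kept after the fix carry error of their own; the amount is given with the fix.

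**Conclusion.** The concern holds. On the literal reading the plan has at least 15 pre-post tests on ten people in a single arm, and the available text gives no means of telling a planned result from the best of them. The chance of at least one false improvement is about 32% with uncorrelated outcomes, falling to about 14% at correlation 0.7. It is somewhat higher if the two interference conditions are analysed separately. These figures rest on an assumed two-sided 0.05 per test, all effects null and equal correlation between outcomes. Even the lowest is more than five times the 2.5% for one pre-named test (14/2.5 = 5.6).

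The missing contrast is a separate, qualitative gap: the interaction is not named, and the time effect does not isolate performance under interference. Both gaps should be closed before outcome data are examined, unless the supplement already does so.

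**What to change.** In the Statistical analyses section, before outcome data are examined:

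1. Name one primary pre-post test at two-sided 0.05 on a measure the sponsor chooses, for example the change in MXE under interference, with direction and cognitive task defined.
2. Name the time-by-task contrast on that measure as the key supporting test.
3. For all remaining tests, choose one of two options: label them exploratory and report each change with its 95% CI; or apply Holm within each outcome family (MXE, accuracy, Toolbox) and state that error is controlled within and not across families.
4. State how the two interference conditions enter each ANOVA, and which post-hoc comparisons are run. Under the Holm option, set each family's size to match.
5. If the supplement already sets a primary test and a correction, cite them here instead.
6. If outcome data have already been examined, label all results exploratory. This must be confirmed: the Participants, Participants' eligibility, Intervention, Cognitive task and Outcome measures sections are partly in the past tense, which raises the question without proving it.

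**Cost.** Wording only, if the data are unexamined. The primary keeps 0.05, with 80% power at n = 10 for a change of about 1.0 SD. Secondary results carry less weight. Under Holm the first step is 0.05/4 = 0.0125 for four tests and 0.05/7 = 0.0071 for seven; power for a 1 SD change at that step falls from about 80% to about 55% and 44%. Across the primary and three Holm families together, a false improvement would still occur in roughly 5% to 10% of null trials, depending on correlation. With independence this is 1 - 0.975 x (1 - 0.00625)^4 x (1 - 0.00625)^4 x (1 - 0.00357)^7 = about 0.096. The families should therefore be labelled secondary. For a study of this size the exploratory label with confidence intervals is the simpler choice.
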